3.1 Changes in the conduct of the study or planned analyses

Not applicable.

4 STATISTICAL METHODOLOGY

4.1 General Statistical Considerations

Data from subjects enrolled in Part 1 will primarily be displayed in listing format and simple statistics summaries. Part 2 data will be summarized in tables according to the treatment groups: Dinutuximab + Irinotecan, Irinotecan, and Topotecan. Unless otherwise specified, Part 1 data will be summarized in the same table as Part 2, but will not be included in any inferential analyses.

Descriptive statistics (n, mean, standard deviation [Std Dev], median, minimum [min], and maximum [max]) for continuous variables, and frequency distributions and percentages for discrete variables will be utilized. In general, the baseline measurement for Part 1 subjects is defined as the last measurement collected prior to the first dose of study treatment. For Part 2 subjects, baseline is defined as the last measurement obtained prior to the date of randomization.

All tabulations of summary statistics, graphical presentations, and statistical analyses will be performed using SAS[®] Version 9.4 or higher.

4.2 Determination of Sample Size

The sample size for Part 1 (approximately 10 subjects) was not based on statistical power calculations. It is considered adequate from a clinical perspective to judge the safety of the combination of dinutuximab and irinotecan, two approved products with known and distinct toxicities.

Power calculations for the randomized portion of the study (Part 2) were based on the primary efficacy objective: to demonstrate significantly longer OS with combination therapy (dinutuximab + irinotecan) vs. irinotecan alone. A 2:2:1 randomization scheme was chosen to increase exposure to dinutuximab and to maximize statistical power for the primary efficacy comparison (dinutuximab combination vs. irinotecan). A total 306 deaths in these two groups will provide approximately 80% power to detect a HR of 0.725 or a 2.3 month gain in median OS (from 6 to 8.3 months); this calculation is based on a log-rank test (2-sided alpha=0.05). If at least 82 deaths occur in the topotecan group, the power will be approximately 65% to detect

the same hazard ratio of 0.725, or a 2.3-month gain in median OS (6 to 8.3 months) with the combination versus topotecan alone (a secondary objective). Overall, a total of approximately 460 subjects (184 each in dinutuximab combination and single-agent irinotecan groups and 92 in the topotecan group) is expected to yield the requisite number of deaths assuming uniform enrollment over 10 months and a follow-up period of 14 months after the last subject is enrolled. The mortality rate will be tracked by the Data Monitoring Committee (DMC) and, if lower than anticipated, additional subjects may be enrolled to maintain original power specifications for the primary efficacy comparison.

Any decision to extend enrollment will be based on the total number of deaths observed, not on the basis of the observed hazard ratio or other unblinded efficacy data. There is no plan to re-estimate the sample size in any manner that would affect the Type 1 error rate.

4.3 Analysis Data Sets

The following analysis sets will be used in the study:

Safety Analysis Set: All subjects who receive at least one dose of any study medication (even a partial dose), grouped by actual treatment received. This set will serve as the basis for the evaluation of all safety data, as well as demographic and baseline disease characteristics, prior cancer therapy, study drug exposure, and dose modifications. Unless noted otherwise, safety data will be summarized or listed separately for Part 1 and Part 2.

Intent to Treat (ITT) Analysis Set: All subjects randomized in Part 2 of the study, as assigned to treatment. The ITT population is the primary population for the analysis of Overall Survival (OS) and will also be used to evaluate all secondary efficacy endpoints and subject characteristics.

Modified Intent to Treat (mITT) Analysis Set: All subjects who were randomized and received at least one dose of the study drug in Part 2 of the study, as assigned to treatment. The mITT population is the primary population for the sensitivity analysis of Overall Survival (OS) and all secondary efficacy endpoints.

Efficacy Evaluable: All subjects randomized in Part 2 of the study who have measurable disease at baseline, receive any amount of the assigned study treatment, and have at least one evaluable post-baseline tumor assessment. Subjects with measurable disease must have at least one measurable lesion. Measurable lesions are defined (according to RECIST) as those that can be accurately measured in at least one dimension (longest diameter to be recorded) as ≥ 20

mm by chest x-ray, as ≥ 10 mm with CT scan, or ≥ 10 mm with calipers by clinical exam. Together with the ITT population, the Efficacy Evaluable group will be used to evaluate ORR and other tumor response endpoints.

Per Protocol Population: All subjects randomized in Part 2 of the study who satisfy the following criteria:

- 1) Completed at least 2 cycles of the assigned treatment
- 2) Qualified for the study based on SCLC diagnosis and prior therapies (i.e., met protocol inclusion criteria 3.1.3, 3.1.4, 3.1.5; did not meet exclusion criterion 3.2.2)
- 3) Received at least 80% of the prescribed study drug (i.e., their average dose during the treatment period was at least 80% of the planned dose).

This population will be used for sensitivity analysis of the primary efficacy endpoint.

4.4 Disposition of Subjects

The disposition of all randomized subjects will be summarized according their status at the time of analysis. This information will include: the number of subjects randomized, treated, discontinued from treatment, discontinued from the study, and continuing in follow-up. The summary will include reasons for discontinuing study treatment or withdrawing from the study as recorded on the eCRF.

Additionally, data listings will identify any subjects who were randomized into the study but did not meet all of the inclusion criteria, met any exclusion criterion, or experienced a major protocol violation during the study.

4.5 Protocol Deviations and Violations

Subjects with major protocol deviations/violations will be listed by treatment group. Protocol deviations will be identified via clinical review based on aspects of study conduct that include (but are not limited to): (1) eligibility criteria; (2) treatment compliance; (3) subject safety; (4) efficacy assessment deviation. Protocol deviations/violations will be closely monitored during the execution of the study and the specific set of protocol deviations/violations that merit consideration in the statistical analysis will be finalized before database lock.

4.6 Demographic and Other Baseline Characteristics

All demographic and baseline characteristics will be summarized for the ITT, mITT, and safety analysis sets using descriptive statistics. The following baseline data will be summarized to describe the study population:

- Demographic and Baseline Characteristics (including age, sex, race/ethnicity, performance status, region of enrollment, tobacco use, height, weight, and body surface area)
- Cancer History and Baseline Pain (e.g., SCLC stage at initial diagnosis, time since initial diagnosis, time since relapse/progression, best response to prior therapy, and pre-existing pain assessment) for each treatment group.
- Tumor Burden at screening visit, defined by:
 - Size of target lesions - sum of recorded diameters for all target lesions
 - Number of non-target lesions (1, 2-3 vs. > 3)
 - Number of involved sites (1, 2-3 vs. > 3) – distinct locations of target and non-target lesions

The 3 treatment groups in Part 2 will be compared using chi-square tests for categorical data and F-test from analysis of variance (ANOVA) for continuous data. Any significant imbalances detected among the treatment groups will be considered in the analysis.

4.6.1 Medical and Surgical History

Medical history data will be coded using the Medical Dictionary of Regulatory Activities (MedDRA), version 20.0 (or higher), and listed by subject.

4.7 Prior/Concomitant Treatment

The WHO Drug Dictionary will be used to classify prior and concomitant medications by therapeutic class and preferred term. Prior medications will be defined as medications taken within 30 days prior to the screening visit that were stopped before the first dose of study medication. Concomitant medications will be defined as any medication taken during the study between the date of the first dose of study medication and 30 days after the date of the last dose (dinutuximab and/or chemotherapy).

4.7.1 Prior Cancer Therapy

The best response to prior cancer therapy and the duration of response to prior first-line platinum therapy (classified as < 3 months or ≥ 3 months) will be summarized by frequency table (i.e., number and percentage of subjects in each category). The type of therapies, details of the administration, and best response to each regimen will be listed for each subject.

4.7.2 Concomitant Treatments

Concomitant medications will be coded using the World Health Organization (WHO) Drug Dictionary, version September 2016 (or higher).

The number and percentage of subjects taking concomitant medications during the treatment period will be summarized by anatomical therapeutic chemical (ATC) and preferred term (PT). Although a subject may have taken the same medication multiple times, the subject is counted only once within an ATC classification. The same subject may contribute to two or more preferred terms in the same ATC classification.

4.8 Study Drug Exposure

4.8.1 Exposure

A frequency table will display the number (%) of patients in each treatment group according to the total number of cycles initiated, as of the cut-off date for analysis. Duration of treatment for each subject will be calculated as the number of days from the date of the first dose of study medication to the date of the last dose taken, inclusive. Duration of treatment, total number of doses administered, cumulative dose, dose intensity, and relative dose intensity will be summarized for each treatment group and each treatment using descriptive statistics (n, mean, median, SD, inter-quartiles, minimum, and maximum) based on the Safety Analysis Set.

For Part 2 subjects, methods for calculating cumulative actual dose, cumulative planned dose, dose intensity, and relative dose intensity for each medication are as follows:

- Cumulative actual dose (mg/m²): Sum of {Starting dose level for each cycle};
- Cumulative planned dose (mg/m²): Sum of {Planned dose level for each cycle}, i.e.;
 - Dinutuximab – (Number of cycles that should have been initiated between the first dose date and the last dose date – 1) x 17.5 + 16, if number of cycles ≥ 2; otherwise, 16 mg/m² if number of cycles = 1;
 - Irinotecan – (Number of cycles that should have been initiated between the first dose date and the last dose date) x 350;
 - Topotecan – (Number of cycles that should have been initiated between the first dose date and the last dose date) x 1.5 x 5;
- Dose intensity (mg/m²/day): Cumulative actual dose / (Last dose date – first dose date + 21);

- Relative dose intensity (%): $\text{Dose intensity} / \{ \text{Cumulative planned dose} / [(\text{Number of cycles that should have been initiated between the first dose date and the last dose date}) \times 21] \} \times 100$.

For each treatment administered, infusion start and stop times, the volume infused, and reasons for any dose reductions or interruptions will be listed for each subject. The number of subjects requiring a dose modification (reduction, delay or interruption) will be summarized descriptively by treatment group.

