6.3. Irinotecan Administration (Part 2: Group A and Group B only)

Irinotecan will be given on Day 1 (+/- 2 days) of each 21-day cycle at a dose of 350 mg/m². Irinotecan is commercially available and should be prepared according to the manufacturer's instructions. Investigators should use the locally approved package insert/summary of product characteristics for additional information such as safety issues, adverse reactions, and storage information. Investigators are strongly encouraged to use anti-emetics other than corticosteroids. If corticosteroids are used, they should be used at the lowest dose and for the shortest period of time judged clinically necessary.

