6.4. Topotecan Administration (Part 2: Group C only)

Topotecan will be given for 5 consecutive days beginning with Day 1 (+/- 2 days) of each 21-day cycle at a dose of 1.5 mg/m². Topotecan is commercially available and should be prepared according to the manufacturer's instructions. Investigators should use the locally approved

package insert/summary of product characteristics for additional information such as safety issues, adverse reactions, and storage information.

A summary of the treatment schedule and dosing can be found in [Table 5](#).

Table 5: Summary of Treatment Schedule and Dosing

Part 1:

| | 1 | 2 | 3 | Cycles† | 5 | ≥6 |
|--|-----|------|------|-------------------------------|--------|--------|
| | 1 | 1 | 1 | Days (Day 1 +/- 2 day window) | 1 | 1 |
| Irinotecan | | | | | | |
| Treatment | X | X | X | X | X | X |
| Dose mg/m ² | 350 | 350 | 350 | 350 | 350 | 350 |
| ⊕ 1 hour (±15 minutes) wait time between end of irinotecan infusion and start of dinutuximab infusion for the 1 st infusion ⊕ | | | | | | |
| Dinutuximab | | | | | | |
| Pretreatment: | | | | | | |
| IV hydration | X | X | X | X | X | X |
| Antihistamines | X | X | X | X | X | X |
| Antipyretics | X | X | X | X | X | X |
| Treatment | X | X | X | X | X | X |
| Dose mg/m ² | 10 | 12*^ | 14*^ | 16*^ | 17.5*^ | 17.5*^ |

†Each cycle is 21 days.

*Dose escalation should occur in 2 mg/m² increments per cycle if maximal pain with prior dose is ≤Grade 1 or Grade 2/3 that in the view of the Investigator is adequately managed and the drug is otherwise tolerated. The maximum dose is 17.5 mg/m² (If this dose is reached, the last dose increment would be 1.5 mg/m²).

Dose de-escalation should occur in 2 mg/m² decrements if toxicity is observed to as low as 8 mg/m²/cycle (See [Section 6.7](#)). If the dose is reduced from 17.5 mg/m², the initial dose decrement would be 1.5 mg/m² (to 16 mg/m²).

^Or tolerated lower dose.

Treatment should continue during the study until RECIST disease progression or intolerable toxicity. See [Section 6.7](#) and [Section 6.9](#) for treatment modifications for dinutuximab and irinotecan, respectively.

[Part 2](#) can be found on the following page.

Part 2:

| | | Cycles† | | | | | | | | | | | | | | |

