6.7.3. Infusion-Related Reactions

| Dinutuximab Treatment Modification | |
|---|--|
| Infusion Reactions Severity (NCI CTCAE v4.03)* | |
| Grade 1 | Mild transient reaction; infusion interruption not indicated; intervention not indicated (e.g., transient flushing or rash, drug fever <38°C) |
| Grade 2 | Therapy or infusion interruption indicated but responds promptly to symptomatic treatment (e.g., antihistamines, NSAIDs, opioid analgesics, IV fluids); prophylactic medications indicated for ≤24 hrs (e.g., rash, flushing, urticaria, dyspnea, drug fever ≥38°C) |
| Grade 3 | Prolonged (e.g., not rapidly responsive to symptomatic medication and/or brief interruption of infusion); recurrence of symptoms following initial improvement; hospitalization indicated for clinical sequelae (e.g., symptomatic bronchospasm, requiring parenteral medication(s), with or without urticaria; allergy-related edema/angioedema, hypotension) |
| Grade 4 | Life-threatening consequences; urgent intervention indicated |

| | |
|---------|---|
| Grade 1 | Decrease dinutuximab infusion rate by 50% and monitor closely for any worsening. |
| Grade 2 | 
Interrupt dinutuximab infusion, administer appropriate therapy (e.g., antihistamines, NSAIDs, IV fluids, steroids, and then restart the dinutuximab infusion with a decrease in the infusion rate of 50% and monitor closely for any worsening.
 
Premedicate in all future cycles with:
 
 • Dexamethasone 20 mg PO administered approximately 12 and 6 hours before dinutuximab, • Diphenhydramine (or its equivalent) 50 mg IV 30 to 60 minutes prior to dinutuximab, and • Cimetidine 300 mg or ranitidine 50 mg IV 30 to 60 minutes before dinutuximab infusion. • If re-starting dinutuximab infusion results in grade 2 or higher toxicity, stop infusion (and record infused dose). 
Reduce dose of dinutuximab by 1 dose level in next cycle.
 |

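### SAP 4.8.1 counts part-given infusions as full doses and, for topotecan only, uses a date interval that keeps full on-time dosing below 100%

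*SAP*

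**What the plan says.** SAP 4.8.1 gives one set of exposure formulas for all Part 2 drugs.

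- Cumulative actual dose (mg/m²) is "Sum of {Starting dose level for each cycle".
- Cumulative planned dose for topotecan is "Number of cycles that should have been initiated between the first dose date and the last dose date) x 1.5 x 5". For irinotecan it is 350 per cycle. For dinutuximab it is 16 in the first cycle and 17.5 in each later one ("x 17.5 + 16, if number of cycles ≥ 2").
- Dose intensity is "Cumulative actual dose / (Last dose date – first dose date + 21" days. Relative dose intensity compares this with planned dose divided by 21 days per planned cycle.

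The protocol gives dinutuximab (6.1) and irinotecan once per cycle: "Irinotecan will be given on Day 1 (+/- 2 days) of each 21-day cycle at a dose of 350 mg/m²". Topotecan differs: "Topotecan will be given for 5 consecutive days beginning with Day 1 (+/- 2 days) of each 21-day cycle". Protocol 6.7.3 tells sites, when a restarted dinutuximab infusion again causes a Grade 2 or higher reaction, to "stop infusion (and record infused dose". SAP 4.8.1 lists the infused volume for each subject but does not use it in the dose sum.

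Separately, Per Protocol criterion 3 in SAP 4.3 reads "Received at least 80% of the prescribed study drug". It is explained there as an average dose of at least 80% of the planned dose.

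**The concern.** Relative dose intensity is the SAP's summary of how fully each drug was delivered, and it is tabulated by arm. It should read 100% when every dose is given in full and on time, and should fall when drug is withheld. The SAP formula breaks the second property for any part-given infusion and the first for topotecan.

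The numerator error makes dinutuximab look better delivered than it was in the subjects whose infusions were stopped, which is where tolerability is worst. The date error makes topotecan look under-delivered even when nothing was missed. A reader comparing arms would see a difference that the formula created.

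**Working it through.** The documents state no numeric dose intensity, so there is no figure to reproduce. The check applies the SAP 4.8.1 formulas to defined dosing patterns.

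**Formula.** Relative dose intensity (RDI) = [actual ÷ (last dose date − first dose date + 21)] ÷ [planned ÷ (21 × n)] × 100, for n cycles.

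**Full dose, on time, drugs given on Day 1 only.** Last minus first dose is 21(n − 1), so the denominator is 21(n − 1) + 21 = 21n. Actual equals planned (350n for irinotecan; 16 + 17.5(n − 1) for dinutuximab). RDI is exactly 100% for every n.

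**Full dose, on time, topotecan.** The last dose falls on Day 5 of the last cycle, so last minus first is 21(n − 1) + 4 and the denominator is 21n + 4. Counting all five daily doses (7.5 mg/m² per cycle, actual and planned), RDI = 21n ÷ (21n + 4):

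- n = 1: 21/25 = 84.0%
- n = 2: 42/46 = 91.3%
- n = 4: 84/88 = 95.5%
- n = 6: 126/130 = 96.9%

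**Stopped dinutuximab infusion.** Take three on-time cycles: 16, then 17.5 stopped part-way, then 16. The last step follows the protocol's one-level reduction after such a reaction (6.7.3) and its 1.5 mg/m² decrement from 17.5 (5.1). Planned dose is 2 × 17.5 + 16 = 51. The interval is 42 + 21 = 63 days, equal to 3 × 21, so the time terms cancel.

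- SAP formula: (16 + 17.5 + 16)/51 = 49.5/51 = 97.1%, whatever was infused.
- Half infused: (16 + 8.75 + 16)/51 = 40.75/51 = 79.9%.

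The documents do not give the fraction infused; one half is an assumption. At one quarter the infused figure is (16 + 4.375 + 16)/51 = 71.3%, and at three quarters (16 + 13.125 + 16)/51 = 88.5%. If the only infusion a subject receives is stopped halfway, the formula gives 16/16 = 100% against 8/16 = 50%.

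**Both errors together, topotecan.** One cycle stopped after Day 3, with the starting level multiplied by five, gives denominator 2 + 21 = 23 and RDI = 21/23 = 91.3%. The dose given is 4.5/7.5 = 60%. A completed cycle scores 84.0%, so the formula ranks the incomplete cycle above the complete one.

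**Check of the remedy.** Measuring to Day 1 of the last cycle plus 21 gives 21n days for all three drugs. Full on-time dosing then scores 100%, and the topotecan cycle stopped after Day 3 scores 60%.

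**The case against.** The case on the other side has several parts.

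- *The drugs in the primary comparison are not affected by the date term.* This is right. A reader might infer that full dosing never reaches 100% for any drug, but irinotecan and dinutuximab do reach it. The topotecan comparisons are labelled exploratory in Protocol 10.1. The numerator rule still applies to every drug.
- *The topotecan excess is small.* A reader might take the 4 days as added in every cycle, which would hold the score at 84% throughout. They are added once per subject, so the shortfall shrinks from 16.0 points at one cycle to 3.1 at six. It matters mainly for short exposures.
- *The missing factor of five is only wording.* Read literally, one daily level of 1.5 per cycle against 7.5 planned would score full topotecan at 16.8% (one cycle) to 19.4% (six). The documents do not support presenting that as the result. The parallel planned-dose line speaks of a dose level for each cycle and expands it to 1.5 x 5, so a per-cycle total is probably meant. Because Protocol 6.10.1 lists daily levels, a clarification is still needed.
- *Partial infusions are not hidden.* Volumes, times and reasons are listed, and SAP Tables 14.1.3.2 and 14.1.3.3 report dose modifications. That is true, but it does not correct the summary statistic.
- *The Per Protocol set is not shown to be affected.* A reader might infer that criterion 3 uses relative dose intensity and so misclassifies subjects. SAP 4.3 makes no such link, and its definition has no time term.

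**Conclusion.** The point holds in limited form. As written, SAP 4.8.1 credits a part-given infusion in full. In the three-cycle dinutuximab example this overstates delivery by 17.2 points (97.1% against 79.9%), assuming half of one infusion was given; the gap is 8.6 points at three quarters infused and 25.7 at one quarter. For topotecan alone, the Day 5 last dose makes full on-time delivery score 84.0% to 96.9% over one to six cycles, on the reading that all five daily doses are counted.

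The consequence is a misleading descriptive exposure table. The primary overall survival test, its power and its estimate do not use these quantities. Whether the Per Protocol sensitivity set is touched depends on how average dose is computed for criterion 3, which the SAP does not say. The dinutuximab example lies above 80% from starting levels and just below it from infused doses.

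**What to change.** Amend SAP 4.8.1 in two places:

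1. Define cumulative actual dose as the sum, over all infusions, of the dose actually infused (mg) divided by BSA. State that all five topotecan days are included.
2. Replace the dose-intensity denominator with Day 1 of the last cycle − first dose date + 21.

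Leave Per Protocol criterion 3 in SAP 4.3 as an average dose against planned dose, and add that it is computed from doses actually infused. Do not tie it to relative dose intensity, because delays would then count as under-dosing. For example, a Group A subject given two full irinotecan doses with a 14-day delay, which Protocol 6.9 allows, would score (700/56) ÷ (700/42) = 75% and be excluded despite receiving the whole prescribed dose.

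The cost is SAP wording and some extra programming. Infused dose or volume and per-cycle BSA (Protocol 8.3) are already collected, so no new data are needed. Reported dinutuximab intensities will be somewhat lower wherever infusions were stopped. Treatment, sample size and type I error are unchanged.
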